9.1 Planned recruitment rate

Initial recruitment projections are one patient per site per month, starting with 30 sites at 12 months after the planned start date, rising to 70 sites by 21 months to the end of initial 5-year funded period. Additional sites may be added as additional funding becomes available.

9.2 Statistical analysis

This section details the general analysis principles and provides a summary of the analytical approach that PANTHER will follow. The full analyses details will be described in the Statistical Analysis Appendix.

9.3 General principles

All between intervention comparisons will be with usual care using contemporaneous participants who were eligible to be randomized to the intervention in question. No comparisons between two active interventions will be undertaken. All inferential analysis will be undertaken in a Bayesian framework.

The flow of participants through the trial and trial results will be reported according to the CONSORT extension for adaptive designs (12).

9.4 Adaptive analyses

Regular adaptive analyses will be carried out to monitor the accrued data. Participant baseline characteristics will be summarised by treatment group and overall using suitable descriptive statistics. Adaptive analysis will include formal stopping rules on the primary outcome which will be triggered by comparing the estimated treatment effect to predefined efficacy and futility boundaries. Summary and between-intervention statistics for secondary and safety outcomes will be presented by treatment group.

The first adaptive analysis will take place at the end of the calendar month when the cumulative number of participants recruited into the larger (hypoinflammatory) subphenotype reaches 240, i.e. 80 per intervention. Thereafter, adaptive analyses will take place every 3 calendar months unless recruitment varies substantially from the planned recruitment rate, in this case the frequency of the adaptive analysis will be revised. The hypoinflammatory subphenotype will be analysed at every adaptive analysis; the smaller (hyperinflammatory) subphenotype will be included in the regular adaptive analysis when its cumulative recruitment total has reached 240 participants and at alternating analyses thereafter, i.e. every 6 months, unless recruitment varies substantially from the planned recruitment rate.

When a new treatment intervention is added to the hypoinflammatory subphenotype, it will be analysed at the first adaptive analysis when it exceeds 80 recruits and at every analysis thereafter until stopping. When a new treatment intervention is added to the

Confidential Page 30 of 48

hyperinflammatory subphenotype, it will be analysed at the first analysis when it exceeds 80 recruits and at alternate analyses thereafter until stopping. The threshold of 80 recruits was chosen to maximise the potential for early stopping (and hence the efficiency of the platform) while also limiting type I error rates, which are higher in smaller samples.

Recruitment to a treatment group within a given subphenotype will be halted when an analysis reveals that an efficacy or futility boundary has been breached, or when the sample size cap is reached or at the discretion of the DMC based on wider review of the trial data. At this point, a final analysis of that treatment within subphenotype with respect to all outcomes will be carried out. After a treatment is stopped a new treatment intervention within that subphenotype may be initiated.

At the first adaptive analysis, confirmation of the validity of the proportional odds assumption will be carried out in each subphenotype. This will be based on the observed distribution of the primary outcome ordinal scale in each treatment intervention compared to usual care. If the proportional odds assumption is not met, then alternative categorisations (i.e. grouping some categories in the ordinal scale together) will be explored. For all adaptive analysis we will examine the consistency of the unadjusted between-group treatment effect across the composite outcome elements (death and organ support free days) for each comparison within each subphenotype.

Very little missing data are expected for the primary outcome; we anticipate minimal loss to follow-up, and eCRFs will be designed so that recording of primary outcome data is mandatory. If the level of missingness does not exceed 5% then the missing data will be assumed to be ignorable, i.e. a complete case analysis will be carried out. If over 5% of outcome data are missing, then the missingness pattern and relationship to other variables will be explored and multiple imputation will be performed.

Statistical stopping triggers

The criteria for stopping recruitment to a treatment group within either subphenotype are based on the probability that the unadjusted odds ratio crosses a predefined value by a predetermined probability threshold. The initial triggers for stopping were identified through extensive simulations to optimise the trial operating characteristics and achieve an appropriate balance between the sample size needed, maximising the power to graduate treatments exceeding the minimal clinically important effect and minimising the chance of graduating treatments with no effect (type I error).

Stopping recruitment to a treatment within either subphenotype will be considered if any of the following conditions are met at any adaptive analysis:

- For efficacy if there is at least an 84% probability of the proportional odds ratio exceeding 1.1.
- For futility if there is at least a 78% probability of the proportional odds ratio falling below 1.075.

These are considered non-binding stopping rules as the DMC will also take into consideration information presented on other outcomes including safety and recruitment data.

If neither of the statistical thresholds are met nor the DMC recommends stopping recruitment to a treatment group at an adaptive analysis, recruitment will stop for futility if the sample size within a treatment group exceeds the frequentist sample size cap for

Confidential Page 31 of 48

London

either subphenotype. This approach prevents perpetual recruitment where there is no or a low likelihood of meeting a trigger. Full simulations details examining the operating characteristics of the proposed design and alternatives for a range of possible threshold values can be found in the statistical design appendices.

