- (d) Declined consent

Additional intervention-specific exclusion criteria will apply which are detailed in each intervention-specific appendix.

TREATMENT/MAIN STUDY PROCEDURES (including treatment duration and follow-up). Therapeutic interventions will be compared with usual care within each subphenotype (see intervention appendices). We will start the platform with 2 interventions and usual care. Additional therapeutic interventions can enter the trial by replacing the initial interventions when they reach criteria for efficacy, for futility, or the maximum sample size or if the scope of the platform expands.

OUTCOME MEASURES

PRIMARY ENDPOINT

28-day organ support-free days, incorporating mortality as a composite on an ordinal scale. Organ support is defined as needing either respiratory or cardiovascular support.

SECONDARY ENDPOINT(S)

- 28-day vasopressor-free days
- 28-day respiratory support-free days ii.
- Receiving new renal replacement therapy iii.
- Progression to invasive mechanical ventilation, extracorporeal membrane İ۷. oxygenation or death among those not receiving that support at baseline
- ICU length of stay ٧.
- Hospital length of stay νi.
- All-cause mortality at 28 and 90 days, vii.
- Safety outcomes (as defined in secondary endpoint section 3.5) viii.
- Serious adverse events ix.
- Physical function (SPPB) at hospital discharge (up to 1 week prior to discharge) Χ.
- Cognitive function (MoCA) at hospital discharge (up to 1 week prior to discharge) χi.

If it is not possible to collect physical function and cognitive impairment measures prior to hospital discharge, this will not be a protocol deviation.

TERTIARY ENDPOINT(S)*

- 14-day delirium and coma free days i.
- Incidence of ICU acquired weakness (MMST and hand grip strength dynamometry ii. and maximal inspiratory pressure) at day 7 and ICU discharge
- Health-related quality of life, (EQ-5D-5L) at 90 days and 180 days iii.
- Hospital Anxiety and Depression Scale (HADS) at 90 days and 180 days ίV.
- Social and Wellbeing (SF-36) at 90 days and 180 days ٧.

Confidential Page 10 of 48

	Protocol No: 175151	Sponsor:	Imperial	College	V 2.1 30.07.2025
		London			
PANTHER					

vi. Impact of Events Scale (6 item) at 90 days and 180 days

vii. Care and wellbeing needs at 90 days and 180 days

viii. Cognitive function (MoCA) at 90 days and 180 days

PHENOTYPING

Initial subphenotypes will be the hyper and hypoinflammatory subphenotypes described in ARDS.

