6.5 Treatment

Treatments within the trial will only be provided while the patients are in the ICU and will be provided and administered by local clinical staff.

Eligible patients will be randomised to usual care or one of the interventions for which they are eligible.

Each subphenotype will have its own control which will be usual care. Usual care will be directed by international treatment guidelines, such as the European Society of Intensive Care Medicine ARDS guidelines. Agreement to comply with these guidelines will be a condition for a site to participate in the trial to ensure standardised best practice usual care. We will collect and report key process measurements of usual care (e.g. compliance with protective lung ventilation and prone ventilation) with feedback and education for sites to achieve compliance with these guidelines if needed.

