9. STATISTICAL ANALYSES

Sample Size and power considerations

The trial has no fixed sample size due to its adaptive design. Extensive simulations were undertaken to estimate the sample size distribution for the initial subphenotypes and two active interventions to be compared to usual care. We report the **expected mean** and **80th percentile** of the simulated distribution, and the **maximum sample size** we will stop recruitment at if no statistical triggers are met.

A **maximum cap** will be used as a guideline by the DMC within each active treatment intervention and subphenotype to ensure the trial does not continue perpetually when there is a low likelihood of a trial trigger being met. The maximum cap is set at the frequentist sample size without any plan for early stopping and the DMC will evaluate the value of continuing after this sample size has been reached.

Usual care is not limited by a maximum sample size and will recruit for the duration of the trial.

The initial sample sizes are as follows:

Sample size	Hypoinflammatory	Hyperinflammatory		
distribution attributes	n per intervention	n per intervention		

Confidential Page 28 of 48

	Protocol No: 175151	Sponsor: London	Imperial	College	V 2.1 30.07.2025
PANTHER					

Expected mean	120	82
80 th percentile	240	156
Maximum cap	504	529

This sample size was calculated based on iterations of different statistical triggers and timing schedules evaluating these against the resulting trial operating characteristic in terms of Type I and Type II error for a realistic range of minimal clinically important differences (MCID). This process resulted in the following optimal design characteristics (triggers and timing of these triggers):

Timing of triggers: Starting at n=80 per intervention and then every 3 months after that in hypoinflammatory. Hyperinflammatory adaptive analysis will be aligned with the hypoinflammatory adaptive analysis, the first taking place after n=80, and then taking place every 6 months in line with the hypoinflammatory analysis.

Statistical Triggers:

- Efficacy will be triggered within intervention and subphenotype if there is at least an 84% probability of the proportional odds ratio exceeding 1.1
- Futility will be triggered if there is at least a 78% probability of the proportional odds ratio falling below 1.075

The sample sizes in the table above are calculated based on the following assumptions:

[figure not shown]

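### The first-look trigger of 240 recruits equals 80 per intervention only if everyone is eligible for both initial interventions, so a restrictive initial arm can be judged below the design's minimum of 80

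*Protocol*

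**What the plan says.** The Trial Summary fixes the initial layout: "We will start the platform with 2 interventions and usual care". Section 9 gives the timing used in the simulated design: "Starting at n=80 per intervention and then every 3 months after that in hypoinflammatory". Section 9.4 turns this into an operating rule based on a stratum total: the first analysis falls at the end of the calendar month in which the number "recruited into the larger (hypoinflammatory) subphenotype reaches 240, i.e. 80 per intervention". The hyperinflammatory stratum also enters at a cumulative total of 240.

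Interventions added later have a different rule, based on the arm itself. In the hypoinflammatory stratum, "it will be analysed at the first adaptive analysis when it exceeds 80 recruits and at every analysis thereafter until stopping". The same section says 80 was chosen to allow early stopping "while also limiting type I error rates, which are higher in smaller samples".

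Partial eligibility is part of the design. Section 6.5 states: "Eligible patients will be randomised to usual care or one of the interventions for which they are eligible". Section 4.1 sets equal ratios between usual care and each intervention the participant is eligible for. Section 6.3 makes intervention eligibility a minimisation factor. Section 9.3 limits each comparison to "contemporaneous participants who were eligible to be randomized to the intervention in question".

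**The concern.** A stratum total of 240 guarantees 80 in each of three groups only when everyone can be allocated to all three. Once some participants are excluded from one intervention, its arm and its usable controls both shrink, and the other groups grow. Section 9.4 sets no arm-level minimum for the two initial arms, although it sets one for every later arm and gives type I error as a reason. An initial arm could therefore be tested against the 84% efficacy trigger at a size the simulated design never used. At stake is whether the stated 17-19% type I error describes the rule that will be run.

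**Working it through.** **Inputs from the protocol.** Two initial interventions plus usual care; equal allocation among eligible options; first look at 240 in the stratum; efficacy trigger P(POR > 1.1) ≥ 0.84; futility trigger P(POR < 1.075) ≥ 0.78; cap 504; 70:30 subphenotype split; one patient per site per month, 30 sites at month 12 rising to 70 by month 21.

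**Assumptions, because the protocol gives no figure.** Share ineligible for one arm; 1 − Σp³ for the outcome distribution (0.9, varied 0.85-0.95); normal prior on the log POR centred at 0 with sd 0.5, 1 or 10 (10 is near-flat).

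**Step 1, the stated figure.** 240/3 = 80. It reproduces under full eligibility for both interventions.

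**Step 2, arm size at exactly 240.** Let a be the share eligible for A only and b the share eligible for B only. Then n_B = 240[(1 − a − b)/3 + b/2], and B's eligible usual-care group has the same expected size.
- b = 0, a = 10%: 240 × 0.90/3 = 72
- b = 0, a = 30%: 240 × 0.70/3 = 56
- b = 0, a = 50%: 240 × 0.50/3 = 40
- a = b = 15%: 240 × (0.70/3 + 0.075) = 74
- a = b = 50%: 240 × 0.25 = 60, the floor when single eligibility is symmetric

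**Step 3, end-of-month timing.** With a linear rise in sites, hypoinflammatory recruitment after eight recruiting months is 0.7 × (8 × 30 + (40/9) × 32) = 267.6. After seven it is 0.7 × (7 × 30 + (40/9) × 24.5) = 223.2. The look therefore falls at about 268, or 89 per arm, and the restrictive arm has about 89(1 − x): 80, 62 and 45 at x = 10%, 30% and 50%. About 10% ineligibility is absorbed.

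**Step 4, error at the first look alone (near-flat prior, POR = 1).** Information with n per arm is I = n(1 − Σp³)/6. The trigger is crossed when z ≥ 0.9945 + ln(1.1)√I.
- n = 89.2: I = 13.4, z = 1.343, error 9.0%
- n = 62.4: I = 9.36, z = 1.286, error 9.9%
- n = 44.6: I = 6.69, z = 1.241, error 10.7%

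**Step 5, error over all looks.** Simulation with 400,000 runs, looks every 3 months to month 48 of recruitment or the cap, 1 − Σp³ = 0.9. Ranges run from futility acted on to not acted on.

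| Ineligible for the arm | First look n | Prior sd 0.5 | Prior sd 1 | Near-flat |
|---|---|---|---|---|
| 0% | 89 | 13.6-14.1% | 16.6-17.2% | 17.6-18.3% |
| 10% | 80 | 14.3-14.9% | 17.4-18.2% | 18.7-19.6% |
| 30% | 62 | 15.6-16.5% | 19.4-20.5% | 20.7-22.0% |
| 50% | 45 | 16.5-17.4% | 21.2-22.6% | 23.1-24.6% |

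Taking 1 − Σp³ as 0.85 or 0.95 moves the weak-prior figures by at most about 0.5 points. A shorter schedule of nine looks gives 18.4-19.1% (sd 1) or 19.8-20.8% (near-flat) at 30%, and 20.0-20.8% or 22.0-22.9% at 50%.

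**Step 6, where the rise comes from.** At 30% ineligible with a near-flat prior, the first-look error rises by about 1 point, but the overall error rises by 20.7 − 17.6 = 3.1 to 22.0 − 18.3 = 3.7 points. Most of the rise comes from having extra looks at small n.

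**Step 7, waiting for the arm's own 80.** At 30% the look at 62 is dropped and the arm enters at 96. At 50% the looks at 45 and 69 are dropped and it enters at 93. Type I error becomes 17.2-17.8% (sd 1) or 18.2-18.9% (near-flat) at 30%, and 17.1-17.6% or 18.2-18.7% at 50%.

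**The case against.** A reader might infer that the true type I error exceeds 17-19%, or that an initial arm will be judged well below 80. The document supports neither as a fact. The share of participants eligible for only one intervention is not given, and neither is the prior variance; section 9.6 says only that the prior is neutral and informative. The 17-19% is stated as conditional on listed assumptions, so other eligibility assumptions extend it rather than prove it wrong. A size well below 80 needs a large, one-sided exclusion.

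The protocol's own tolerance also counts. Section 9 accepts a type I error of around 20% for this phase 2 screen, so the 30% case is close to what was accepted and only the 50% case clearly departs. With prior sd 0.5 nothing exceeds 19%. The triggers are non-binding, and section 9 shows that 80 per intervention was intended.

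These points limit the size of the problem but do not remove it. A prior sd of 0.5 gives about 14% under full eligibility and so does not match the stated range, whereas weak priors do; and the error rises as eligibility falls under every prior tried. The stated bounds already cover futility being acted on or not, and DMC discretion does not restore the missing minimum. Intent in section 9 does not settle the matter either, because section 9.4 is the operating rule and gives a different count.

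**Conclusion.** The equality in section 9.4 is wrong under the partial eligibility the protocol foresees, and the initial arms lack the arm-level minimum that added arms have. Type I error can exceed 17-19%, depending on eligibility share and prior. With weak priors and one-sided ineligibility it is about 18.5-22% at 30% and 20-25% at 50%; there is little or no excess at 10-15%, and none with prior sd 0.5.

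The figures rest on an assumed outcome distribution, prior and eligibility share. Under full eligibility the simulation is consistent with the stated type I error but gives power of about 90-93% with weak priors, against 92-96% stated, so it is not an exact copy of the design. The hyperinflammatory stratum has the same gap in its rule, but its error was not simulated. This is a modest but real fault in a decision rule and should be corrected.

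**What to change.** In section 9.4, replace the 240-total condition in both subphenotypes with the rule already written for added interventions: each initial intervention enters the adaptive analyses at the first scheduled look at which it has at least 80 recruits of its own, with its eligible concurrent usual-care group. If everyone is eligible for both, 240 still gives about 80 per arm and almost nothing changes.

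The text change is about one sentence. The operational cost is a later first look for the restrictive arm, by one interval at 30% and two at 50% ineligible in the working above. Intervals are 3 months in the hypoinflammatory stratum and possibly up to 6 months in the hyperinflammatory stratum. If the sponsor prefers to keep the 240 trigger, the alternative is to report operating characteristics under plausible partial eligibility.

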3.5 Secondary Endpoints

- 28-day vasopressor-free days i.
- 28-day respiratory support-free days ii.
- lii. Receiving new renal replacement therapy
- iv. Progression to invasive mechanical ventilation, extracorporeal membrane oxygenation or death among those not receiving that support at baseline
- ICU length of stay ٧.
- vi. Hospital length of stay
- vii All-cause mortality at 28 and 90 days
- viii. Safety outcomes:-
 - Elevated Creatine Kinase more than 10 times the upper limit of normal
 - Alanine Transaminase or Aspartate Transaminase more than 8 times the upper limit of normal
 - Severe thrombocytopenia, out of keeping with clinical disease
 - Severe neutropenia, out of keeping with clinical disease
 - Serious infection defined as a positive blood cultures requiring treatment and pulmonary aspergillosis requiring treatment
 - Venous thromboembolism
 - Stroke
 - Myocardial infarction

Confidential Page 16 of 48

	Protocol No: 175151	Sponsor:	Imperial	College	V 2.1 30.07.2025
	1 1010001110. 110101	London	mpona	ooogo	7 2.1 00.07.2020
		London			
PANTHER					

- Ischaemic bowel
- Gastrointestinal perforation
- Clinically important gastrointestinal (GI) bleeding. Defined as overt bleeding on GI endoscopy, developing as a complication in the ICU and accompanied by 1 or more of the following features within 24 hours:-
 - Spontaneous drop of systolic, mean arterial pressure or diastolic blood pressure of 20mmHg or more
 - o Start of vasopressor or a 20% increase in vasopressor dose
 - Decrease in haemoglobin of at least 2 g/dl
 - o Transfusion of 2 unites of packed RBC or more
- ix. Serious adverse events
- x. Physical function (SPPB) at hospital discharge (up to 1 week prior to discharge)
- xi. Cognitive function (MoCA) at hospital discharge (up to 1 week prior to discharge)

If it is not possible to collect physical function and cognitive impairment measures prior to hospital discharge, this will not be a protocol deviation.

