9.6 Primary Modelling Approach for Adaptive and Final Analysis

'Adaptive analyses' are those performed regularly to make decisions for changing the trial. 'Final analysis' will performed once an intervention arm has met a statistical trigger and the DMC have confirmed stopping.

The primary efficacy analyses will be based on single Bayesian proportional odds logistic regression models fitted for each subphenotype. The primary **adaptive analysis** will be **unadjusted** and the **final primary efficacy** analyses will be **adjusted** for minimisation covariates and other strong prognostic variables. For adaptive and final analyses the posterior distribution of the proportional odds ratio (POR) associated with each treatment (relative to usual care) will be estimated using Markov Chain Monte Carlo techniques and the mean and 95% credible interval reported, and for the adaptive analyses the probability of exceeding the relevant statistical triggers (see above in Statistical stopping triggers). POR>1 relative to usual care indicates a favourable treatment effect. We will also examine the treatment effect across both subphenotypes by combining the data across

Confidential Page 32 of 48

subphenotypes and using the same regression model, reporting the POR and 95% credible interval. Full details of the adaptive and final analyses will be specified in the corresponding SAPs.

The primary analysis will use neutral informative prior distribution on the treatment effect where the variance will be chosen to only make extreme results highly unlikely. Where external trial evidence is available on the effect of an intervention in a particular subphenotype, a sensitivity analysis will include this evidence in the analysis using an informative prior distribution. Unadjusted and adjusted treatment effects will be presented in all reports.

Secondary efficacy endpoints

Secondary efficacy outcomes will be summarised and tabulated and unadjusted treatment effects will be calculated at each adaptive analysis. Full model-based analyses will be performed only at the final analysis for each treatment intervention in each subphenotype (i.e. once recruitment to a treatment group within a subphenotype is stopped).

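### The final analysis of a stopped arm on all outcomes is tied to the halt of recruitment, with no condition that day-28 and day-90 follow-up be complete

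*Protocol*

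**What the plan says.** The timing of the final analysis is stated three times in the Protocol.

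- Section 9.4: "Recruitment to a treatment group within a given subphenotype will be halted when an analysis reveals that an efficacy or futility boundary has been breached". Two further routes to a halt are named, the cap and the DMC's discretion. It continues: "At this point, a final analysis of that treatment within subphenotype with respect to all outcomes will be carried out".
- Section 9.6, modelling approach: the final analysis is "performed once an intervention arm has met a statistical trigger and the DMC have confirmed stopping".
- Section 9.6, secondary efficacy endpoints: full models are fitted only at the final analysis, "i.e. once recruitment to a treatment group within a subphenotype is stopped".

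The outcomes have different horizons. The primary endpoint (3.4) is organ support-free days to day 28, with every death scored -1. Section 3.5 lists "All-cause mortality at 28 and 90 days" among the secondary endpoints. Section 3.6 has tertiary endpoints at 90 and 180 days.

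The first adaptive analysis is timed by recruitment, not by completed outcomes: it falls at the end of the month in which the "cumulative number of participants recruited into the larger (hypoinflammatory) subphenotype reaches 240, i.e. 80 per intervention".

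On missing primary data, section 9.4 allows a complete-case analysis up to 5% missing. Beyond that, the rule moves to imputation: "If over 5% of outcome data are missing, then the missingness pattern and relationship to other variables will be explored and multiple imputation will be" …

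**The concern.** Recruitment runs up to the analysis that stops the arm, so the most recent participants cannot yet have 28-day, 90-day or 180-day outcomes. Followed as written, the timing rule has the definitive adjusted analysis done before those data can exist.

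Three things are at stake.

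- **Content.** Ninety-day mortality would be reported with a large part of the arm not yet at day 90.
- **Selective availability.** A death has a primary score as soon as it occurs. A survivor's score is settled only at day 28, since section 3.4 counts from the last time support was received. Among recent recruits the scores at hand would therefore be mainly deaths, and using them without the pending survivors is not ignorable.
- **Fresh information.** The adaptive analysis is unadjusted and the final one adjusted. Run on the same data cut, the final analysis adds covariates but almost no new outcomes. Completed follow-up would be a modest new check on an early boundary crossing.

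The 5% rule adds an ambiguity, because it does not say whether follow-up still running counts as missing.

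**Working it through.** **The plan's own figure.** Two interventions plus usual care at 80 each: 3 × 80 = 240, as section 9.4 states. The protocol gives no figure for incomplete follow-up, so it is derived here.

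**Inputs**
- One patient per site per month; 30 sites at month 12, rising to 70 by month 21 (section 9.1). The shape of the rise is not stated; linear is assumed.
- 70:30 hypoinflammatory to hyperinflammatory (section 9, sample size assumptions), applied to all recruits.
- Three equal groups throughout.
- Analyses at month end, then every 3 months (section 9.4).
- 28, 90 and 180 days taken as 0.92, 2.96 and 5.91 months.

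**Formula.** With t in months after month 12 and p = 0.7 or 0.3:
- for t ≤ 9, N(t) = p × (30t + (20/9)t²)
- for t > 9, N(t) = p × (450 + 70(t − 9))
- share short of day d = [N(t) − N(t − d)] / N(t)

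**First hypoinflammatory analysis.** N reaches 240 at t = 7.4 (month 19.4), so the analysis falls at month 20, t = 8.
- N(8) = 0.7 × (240 + 142.2) = 268
- N(7.08) = 227, so (268 − 227)/268 = 15.3% are short of day 28, about 41 people
- N(5.04) = 145, so 45.6% are short of day 90, about 122 people
- the same step for 180 days gives 81.1%

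Cut at exactly 240 recruits, the day-28 and day-90 shares are 16.3% and 48.5%.

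**Other halts (linear ramp)**

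| Halt | Recruits in stratum | Short of day 28 | Short of day 90 |
|---|---|---|---|
| Hypoinflammatory, 1st analysis | 268 | 15.3% | 45.6% |
| Expected mean, 120 per group | 360 | 12.5% | 38.4% |
| Hypoinflammatory, 2nd | 413 | 10.9% | 34.7% |
| Hypoinflammatory, 3rd | 560 | 8.0% | 25.9% |
| Hypoinflammatory, 4th | 707 | 6.4% | 20.5% |
| Hypoinflammatory, 5th | 854 | 5.3% | 17.0% |
| Hypoinflammatory, 6th | 1001 | 4.5% | 14.5% |
| Hypoinflammatory cap, 504 per group | 1512 | 3.0% | 9.6% |
| Hyperinflammatory, 1st (month 26) | 240 | 8.1% | 25.9% |

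For example, at the second analysis (t = 11) N = 0.7 × (450 + 140) = 413. The last 28 days contribute 0.7 × 70 × 0.92 = 45, and 45/413 = 10.9%.

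**Sensitivity to the ramp, first hypoinflammatory analysis (day 28; day 90).** Monthly steps 15.4–16.0%; 46–48%. Late jump to 70 sites 15.7–18.8%; 38–41%. Flat 70 sites 18–19%; 59–60%. Flat 30 sites 8%; 25–26%.

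**The case against.** The best defence is that these sentences name the event that prompts the final analysis, not the date of the data cut. An analysis of all outcomes can only be done once they exist, section 6.6 plans follow-up at 90, 180 and 365 days without ending it when an arm stops, and section 9.6 leaves full details to SAPs not shown here. That reading is possible, and it may be what is meant. But the protocol does not merely leave the matter open: it states a timing three times, each anchored to the trigger or the halt, and adds no follow-up condition. An SAP that waited would depart from that wording.

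Four stronger readings are tempting and are not supported.

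- **That 15% and 46% apply to any halt.** They hold for the earliest hypoinflammatory halt; the table shows how they fall. Early halts are still a main case, since the expected mean is 120 per intervention against a first analysis at 80.
- **That pending outcomes would be multiply imputed.** Section 9.4 does not say so. It discusses missing data alongside minimal loss to follow-up and mandatory data entry, and expects very little. The rule is silent on follow-up still running, and that silence is the defect.
- **That the final analysis decides which drugs graduate.** Section 9.4 links graduation to the stopping triggers, which use the unadjusted adaptive analysis.
- **That adaptive analyses should also be restricted to participants who have reached day 28.** That would cut the first one to about 240 × 0.837 / 3 = 67 to 268 × 0.847 / 3 = 76 per group, below the 80 that section 9.4 says was chosen partly to limit type I error. It is a separate trade-off and no part of this point.

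**Conclusion.** The point stands as a fault in a stated timing rule. Sections 9.4 and 9.6 place the final analysis at the halt or the confirmed trigger, and nothing makes it wait for outcomes that recent recruits cannot yet have. The exposure is greatest at the first hypoinflammatory analysis and smallest at the cap. On the linear ramp, the share short of day 28 is above 5% at the first five hypoinflammatory analyses and at the first hyperinflammatory one.

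The sizes rest on the assumed ramp, the 70:30 split applied to all recruits, and three groups recruiting throughout. Two limits apply. The share with no primary score is somewhat below the share short of day 28, because deaths already have a score. The time for DMC confirmation is not given, and recruitment continuing during it would leave a similar share incomplete.

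**What to change.** In sections 9.4 and 9.6, state that:

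1. the halt of recruitment, by whichever route, or the confirmed trigger prompts the final analysis;
2. the analysis is run once the last participant in the stopped arm and its concurrent usual-care comparators has completed day 28 for the primary outcome and day 90 for the secondary outcomes;
3. 180-day outcomes are reported when complete;
4. follow-up not yet due does not count as missing for the 5% rule.

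If this is already the intent, a sentence in each section confirms it. It is best settled before the first adaptive analysis.

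The cost is wording, and a final report about 1 month later for the primary outcome and about 3 months later for the secondary outcomes. No extra participants are needed, and the decision to halt recruitment and the timing and size of the adaptive analyses are unchanged.
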